## 1. Protocol Summary

### 1.1. Synopsis

**Protocol Title:** A Multicenter, Open Label Study Assessing the Efficacy of AJOVY® (fremanezumab-vfrm) on Interictal Migraine Related Burden

### Objectives and Endpoints:

Objectives	Endpoints
Primary	
1. To evaluate the efficacy of fremanezumab-vfrm on interictal migraine related burden between 50% responders and non-responders, via change in Migraine Interictal Burden Scale (MIBS-4) score during the 12-week treatment phase.	1. Change in monthly Migraine Interictal Burden Scale (MIBS-4) scores from baseline to each 4-week treatment period during the 12-week treatment period comparing between 50% responders and non-responders within subjects treated with fremanezumab-vfrm.
Secondary	
To evaluate the efficacy of fremanezumab-vfrm between 50% responders and non-responders on the following parameters during the 12-week treatment phase: 
 
1. Change in migraine days
 
2. Change in Neuro-QoL Sleep Disturbance Short Form (SDSF)
 
3. Change in General Self-Efficacy Short Form (GSE-SF)
 
4. Change in PROMIS-29
 
5. Change in Work Productivity and Activity Impairment- Migraine (WPAI-M)
 
	Change from baseline to each 4-week treatment period during the 12-week treatment period comparing between 50% responders and non-responders within subjects treated with fremanezumab-vfrm on the following: 
 
1. Number of migraine days
 
2. Neuro-QoL Sleep Disturbance Short Form (SDSF) scores
 
3. General Self-Efficacy Short Form (GSE-SF) scores
 
4. PROMIS 29 scores
 
5. Work Productivity and Activity Impairment- Migraine (WPAI-M) scores
 

This document, including any source code, is the property of [Clinvest Research LLC](#), and may contain proprietary, confidential, or legally privileged information. No part of this report, or any information contained therein, may be disseminated without the written consent of [Clinvest Research LLC](#).

Objectives	Endpoints

6. Change in Brief Measure of Worry Severity (BMWS)
 
7. To evaluate the safety and tolerability of subjects treated with fremanezumab-vfrm
	
6. Brief Measure of Worry Severity (BMWS) scores
 
7. Safety and tolerability of fremanezumab-vfrm in study participants via collection of adverse events and safety evaluations.


Exploratory
 
To evaluate the efficacy of fremanezumab-vfrm between 50% responders and non-responders on the following parameters during a 12-week treatment phase:
 
 
1. Change in activity and sleep measured through a wearable device
 
	
1. Change from baseline to each 4-week treatment period during the 12-week treatment period comparing between 50% responders and non-responders within subjects treated with fremanezumab-vfrm on activity and sleep measured through a wearable device.

### Overall Design:

This is a single group, multicenter, open-label study with a study population of patients who meet International Classification of Headache Disorders 3rd edition (ICHD-III) criteria for migraine with or without aura and have 4 to 22 migraine days per month.

### Disclosure Statement:

This is a single-group supportive care study with one arm and no masking.

### Number of Participants:

A maximum of 40 participants will be enrolled to study intervention.

**Note:** "Enrolled" means a participant's, or their legally acceptable representative's, agreement to participate in the clinical study following completion of the informed consent process and the 4-week run-in period. Potential participants who are screened for the purpose of determining eligibility for the study, but do not participate in the study via at least one administration of IP, are not considered enrolled.

**Intervention Groups and Duration:**

**All participants in this single-group study will complete a 4-week run-in period. After the run-in period, eligible participants will be enrolled to study intervention and enter a 12-week treatment period.**

**Data Monitoring Committee: No**

## 1.2. Schedule of Activities (SoA)

Procedure	Screening	Treatment				Early Discontinuation
	Visit 1 Day -33 to Day -28	Visit 2 (Enrollment) Day 1	Visit 3 Day 29 ± 3	Visit 4 Day 57 ± 3	Visit 5 Day 85 ± 3	
Informed consent	X					
Height	X					
Weight	X	X	X	X	X	X
Vital signs	X	X	X	X	X	X
Demography	X					
Physical examination	X	X	X	X	X	X
Neurological examination	X					
Medical history (includes migraine history and substance usage)	X					
Prior and concomitant medications history	X					
Urine pregnancy test (WOCBP only)	X	X	X	X	X	X
Laboratory assessments (CMP)	X				X	X
12-lead ECG	X				X	X

This document, including any source code, is the property of [Clinvest Research LLC](#), and may contain proprietary, confidential, or legally privileged information. No part of this report, or any information contained therein, may be disseminated without the written consent of [Clinvest Research LLC](#).

Procedure	Screening	Treatment				Early Discontinuation
	Visit 1 Day -33 to Day -28	Visit 2 (Enrollment) Day 1	Visit 3 Day 29 ± 3	Visit 4 Day 57 ± 3	Visit 5 Day 85 ± 3	
PHQ-9	X	X	X	X	X	X
Inclusion and exclusion criteria	X	X				
Dispense activity tracker	X					
Dispense diary URL and instructions	X					
Migraine Interictal Burden Scale (MIBS-4)	X	X	X	X	X	X
Neuro-QoL Sleep Disturbance Short Form (SDSF)		X	X	X	X	X
PROMIS-29		X	X	X	X	X
Work Productivity and Activity Impairment-Migraine (WPAI-M)		X	X	X	X	X
General Self-Efficacy Short Form (GSE-SF)		X	X	X	X	X
Brief Measure of Worry Severity (BMWS)		X	X	X	X	X
AE review		X	X	X	X	X
SAE review		X	X	X	X	X
Diary review		X	X	X	X	X
Concomitant medication review		X	X	X	X	X
IP injection		X	X	X		

This document, including any source code, is the property of [Clinvest Research LLC](#), and may contain proprietary, confidential, or legally privileged information. No part of this report, or any information contained therein, may be disseminated without the written consent of [Clinvest Research LLC](#).

## 2. Introduction

### 2.1. Study Rationale

This study is being conducted to evaluate the efficacy and safety of fremanezumab-vfrm on interictal migraine related burden in adult participants age 18 to 65 years old, who meet International Classification of Headache Disorders 3rd edition (ICHD-III; Appendix 5) criteria for migraine with or without aura and have 4 to 22 migraine days per month.

### 2.2. Background

The burden of Migraine can extend well beyond the pain phase and affect more than just work and school attendance. Patients with frequent Episodic Migraine and Chronic Migraine are known to experience the impact of migraine even on days they do not have migraine pain or associated symptoms such as nausea, photophobia, or phonophobia. Most of the focus of migraine management is placed on migraine pain and associated symptom relief and the interictal burden of migraine is often overlooked.

Individuals experiencing frequent migraine attacks regularly find themselves engaged in preparatory or compensatory behaviors, hoping to minimize lost productivity or compromised quality of life, even before attacks begin. These types of behaviors originate from the fear and dread of the inevitable migraine attacks to come and lead to a significant diminution of quality of life before the pain has even started. Patients frequently cancel plans with family and friends or avoid making commitments in the first place based on their anticipation of a migraine episodes. Even worse, these fears and behavior changes also tend to exacerbate co-occurring conditions such as anxiety, depression, and sleep disorders, further contributing to poor quality of life. Unfortunately, migraine prevention trials have traditionally focused on reduction of migraine days as a primary endpoint and have largely ignored the significant health and lifestyle burdens also associated with migraine and associated symptoms.

### 2.3. Significance

This study aims to capture changes in functional impact, including but not limited to the assessment of the interictal burden of migraine after participants begin treatment with fremanezumab-vfrm. In addition to using a variety of scales to capture these changes this study will use activity trackers to allow detailed monitoring of daily activity and sleep patterns. This approach has been used in a variety of clinical trials over a wide range of disease states with success and its addition will enrich the results obtained through administration of traditional questionnaires. Specific assessments of worry, work productivity, and self-efficacy will

complement the overall impact of patients' lives directly and indirectly related to response to CGRP blockade. It is hypothesized that participants treated with fremanezumab-vfrm will demonstrate improvements in a variety of measures of daily activity and attitudes. Results from this study will be a significant contribution to the medical literature and bring value to providers as they manage expectations with patients regarding the functional impact of fremanezumab-vfrm on migraine prophylaxis efforts. Moreover, this study aims to bridge the gap between the traditional focus on reduction of migraine days as a primary endpoint and the numerous other significant health and lifestyle burdens also associated with migraine and associated symptoms.

#### **2.4. Benefit/Risk Assessment**

Detailed information about the known and expected benefits and risks and reasonably expected adverse events of fremanezumab-vfrm may be found in the Package Insert.

### 3. Objectives and Endpoints

Objectives	Endpoints

Primary
 
1. To evaluate the efficacy of fremanezumab-vfrm on interictal migraine related burden between 50% responders and non-responders, via change in Migraine Interictal Burden Scale (MIBS-4) score during the 12-week treatment phase.
	
1. Change in monthly Migraine Interictal Burden Scale (MIBS-4) scores from baseline to each 4-week treatment period during the 12-week treatment period comparing between 50% responders and non-responders within subjects treated with fremanezumab-vfrm.

Secondary
 
To evaluate the efficacy of fremanezumab-vfrm between 50% responders and non-responders on the following parameters during the 12-week treatment phase:
 
1. Change in migraine days  2. Change in Neuro-QoL Sleep Disturbance Short Form (SDSF)  3. Change in General Self-Efficacy Short Form (GSE-SF)  4. Change in PROMIS-29  5. Change in Work Productivity and Activity Impairment- Migraine (WPAI-M)  6. Change in Brief Measure of Worry Severity (BMWS)  7. To evaluate the safety and tolerability of subjects treated with fremanezumab-vfrm
	
Change from baseline to each 4-week treatment period during the 12-week treatment period comparing between 50% responders and non-responders within subjects treated with fremanezumab-vfrm on the following:
 
1. Number of migraine days  2. Neuro-QoL Sleep Disturbance Short Form (SDSF) scores  3. General Self-Efficacy Short Form (GSE-SF) scores  4. PROMIS 29 scores  5. Work Productivity and Activity Impairment- Migraine (WPAI-M) scores  6. Brief Measure of Worry Severity (BMWS) scores  7. Safety and tolerability of fremanezumab-vfrm in study participants via collection of adverse events and safety evaluations.

This document, including any source code, is the property of [Clinvest Research LLC](#), and may contain proprietary, confidential, or legally privileged information. No part of this report, or any information contained therein, may be disseminated without the written consent of [Clinvest Research LLC](#).

Objectives	Endpoints

Exploratory
 
To evaluate the efficacy of fremanezumab-vfrm between 50% responders and non-responders on the following parameters during a 12-week treatment phase:
 

1. Change in activity and sleep measured through a wearable device

	

1. Change from baseline to each 4-week treatment period during the 12-week treatment period comparing between 50% responders and non-responders within subjects treated with fremanezumab-vfrm on activity and sleep measured through a wearable device.

This document, including any source code, is the property of [Clinvest Research LLC](#), and may contain proprietary, confidential, or legally privileged information. No part of this report, or any information contained therein, may be disseminated without the written consent of [Clinvest Research LLC](#).

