### 9.2. Sample Size Determination

To determine the needed sample size for this study we utilized G\*Power Version 3.1.9.3 to conduct a power analysis for the Primary Endpoint analysis (repeated measures ANOVA, within-between interaction) comparing baseline MIBS-4 scores to treatment month(s) MIBS-4 scores between 50% responders and non-responders. Based on prior research, we expect an approximate equal proportion of responders and non-responders in this open-label study. The power analysis indicated that a total of 36 subjects would be adequate to detect a medium effect ( $f= 0.25$ ), with alpha set at 0.05, and a power of .95. To account for a 10% early withdrawal rate, a total of 40 subjects should be enrolled in the study.

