### 9.4. Statistical Analyses

The statistical analysis plan (SAP) will be finalized prior to database lock and it will include a more technical and detailed description of the statistical analyses described in this section. This section is a summary of the planned statistical analyses of the most important endpoints including primary and key secondary endpoints. In case of a discrepancy, the SAP will supersede the protocol.

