#### **9.4.1. General considerations**

An alpha of .05 will be used for statistical significance for all statistical tests. All statistically significant multivariate analyses will be followed by univariate post-hoc tests. Appropriate multiple comparison adjustments will be made if needed. A Last Observation Carried Forward (LOCF) method will be utilized to impute missing data where appropriate.

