#### **9.4.3. Secondary endpoint(s)**

Data for each of the secondary outcome measures will be statistically analyzed for within and between group changes via analysis of variance (ANOVA), *t*-tests, or chi-square tests as appropriate.

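### The term 50% responder is undefined; if it means a halving of diary migraine days, the between-group test of migraine-day change largely reflects how the groups were sorted

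*Combined protocol and SAP*

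**What the plan says.** Section 3, repeated in the synopsis, states the secondary objective as "To evaluate the efficacy of fremanezumab-vfrm between 50% responders and non-responders on the following parameters during the 12-week treatment phase". The matching endpoints are changes from baseline to each four-week period, "comparing between 50% responders and non-responders within subjects treated with fremanezumab-vfrm on the following", and the list opens with "1. Number of migraine days". Migraine days come from the daily headache diary (section 8.1.2).

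On analysis, section 9.4.3 says "Data for each of the secondary outcome measures will be statistically analyzed for within and between group changes", using ANOVA, t-tests or chi-square tests. Section 9.4.1 adds "An alpha of .05 will be used for statistical significance for all statistical tests" and "A Last Observation Carried Forward (LOCF) method will be utilized to impute missing data where appropriate".

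The same responder split defines the null hypothesis (9.1), the sample size (9.2), the primary analysis (9.4.2) and the exploratory wearable endpoint (section 3). Section 9.2 states "Based on prior research, we expect an approximate equal proportion of responders and non-responders in this open-label study". None of these places, nor the abbreviations list, says which measure must fall by 50%, over which window, or how missing diary days and early leavers are handled. Section 9.4 leaves technical detail to an SAP due before database lock: "In case of a discrepancy, the SAP will supersede the protocol". No separate SAP text is supplied.

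**The concern.** The likeliest reading of 50% responder is at least a 50% fall in diary migraine days. Section 4.1 supports it by saying that the run-in diaries are used to assess treatment response as well as symptoms. On that reading, participants are sorted by their percentage fall in migraine days and the two groups are then tested for a difference in change in migraine days. The grouping variable and the outcome come from the same diary counts, so a small p-value is expected even when no participant truly responds better than another.

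Two things are at stake. First, the objective uses the language of efficacy, so a significant result on this item could be reported as an efficacy finding. Second, the undefined split also decides who is in which group for the primary MIBS-4 comparison. The study is open-label, and the protocol requires the SAP only before database lock, so the definition need not be fixed before outcomes are seen.

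**Working it through.** **1. The plan's own figure.** Section 9.2 gives f = 0.25, alpha 0.05, power 0.95, 36 evaluable and 40 enrolled after 10% withdrawal. It does not state the number of measurements, their correlation or the sphericity correction. Assume two groups, m = 4 visits, correlation 0.5 and epsilon 1:

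- noncentrality = f² × N × m / (1 − rho) = 0.0625 × 36 × 4 / 0.5 = 18
- df = (2 − 1)(4 − 1) = 3 and (36 − 2)(4 − 1) = 102
- power = 0.952; 36 / 0.90 = 40

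The figure reproduces, so this point is not about sample size. The expected equal split gives 18 against 18.

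**2. Why the sorting drives the test.** Let B be run-in migraine days, F the treatment-period count and D = F − B the endpoint. A responder has F ≤ B/2, that is, D ≤ −B/2. If everyone had the same B, the two groups could not overlap on D at all. They overlap only because B may range from 4 to 22. A participant going from 4 to 2 days is a responder with D = −2, while one going from 22 to 12 (a 45% fall) is a non-responder with D = −10. Rejection is therefore very likely but not certain, and its frequency depends on the diary distribution.

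**3. Simulation.** The documents give no diary means or variances, so these inputs are assumptions:

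- binomial counts out of 28 days
- true baseline of 3–22 days in three shapes (uniform, low-skewed and high-skewed beta), with the run-in count screened to 4–22
- log-normal month-to-month variation with log SD 0.1, 0.25 or 0.4
- N = 36 and an identical true 48% fall in everyone unless stated, which gives a near-equal split
- two-sided t-test at 0.05 on absolute change (the protocol does not state sidedness)

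| Response window and period tested | Trials rejecting |
|---|---|
| Tested month is itself the window | about 99–100% |
| Weeks 1–12 window, 12-week mean | about 93–100% |
| Weeks 1–12 window, single months | about 83–100% |
| Weeks 1–12 window, single months, artificial two-cluster baseline with binomial noise only (separate run) | about 70% |
| Month-3 window, months 1–2, no between-patient spread | about 18–45% |
| Month-3 window, months 1–2, spread in true response (log-SD 0.3–0.5) | about 54–98% |
| Groups formed at random | about 5% |

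In the spread row, part of the difference is real, because patients then do differ in response. If one repeated-measures ANOVA interaction is used instead of separate tests, with no spread it rejects in 88.5–99.8% under a weeks 1–12 window and 97.7–99.9% under a month-3 window.

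**4. How much the definition matters for the primary groups.** Weeks 1–12 and month-3 definitions put about 23–25% of participants in different groups when there is no spread, and about 14–22% with spread.

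**5. Missing diary days.** Suppose missing days were counted as migraine-free, a rule the protocol does not propose. The true fall needed to count as 50% would then be:

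- 1 − 0.5/0.80 = 37.5% with a complete run-in and 80% entry in treatment (the section 8.1.2 minimum)
- 1 − 0.5 × 23/28 = 58.9% with a run-in at the section 4.1 minimum of 23/28 and complete treatment diaries
- 1 − 0.5 × (23/28)/0.80 = 48.7% with both at their minimum

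**The case against.** **The SAP may settle it.** Section 9.4 assigns detail to a document that supersedes the protocol and is not supplied. This stands: what can be said firmly is that the protocol is silent, and the circular test is conditional on the diary reading. A MIBS-4 definition would remove the overlap here but move it to the primary endpoint.

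**The item is descriptive in spirit and minor.** The objective itself names the responder contrast, the one-arm design is openly stated, and section 2.3 places the study's interest beyond migraine-day reduction. This stands as a limit on severity. It does not remove the planned test, because section 9.4.3 covers each secondary measure.

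**Stronger readings a reader might infer.**

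- That every period inside the window is practically certain to be significant. This fits a month that is its own window. It is too strong for single months in a weeks 1–12 window (about 83–100%, and about 70% in the artificial case). It also weakens away from an equal split: with an identical 30% fall and 7–30% responders, single months reject in 45–98%.
- That periods outside the window are usually not significant. This holds only when patients do not differ in true response.
- That missing diary days would move many participants between groups. A shift of 6.5–12.7 of 40 arises only with complete run-in diaries, everyone at exactly 80% entry in treatment, and missing days counted as migraine-free. At both diary minimums about 1–2 move, and at equal 90% entry none do. The documents do not support the large figure as a general one.

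**Conclusion.** The point holds in conditional form. The supplied protocol does not define its grouping factor. On the natural diary reading, the between-group p-value for migraine days is largely a product of the sorting rule, rejecting in about 83–100% of trials for periods inside the response window against about 5% for random groups, outside the artificial two-cluster case. These rates rest on assumed diary distributions, 36 participants, near-equal groups and an identical true 48% fall.

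The direct consequence is limited to one of seven secondary items; no sample size or interim rule depends on it. That no responder contrast isolates a drug effect is a limit of the one-arm design as a whole. What is specific here is the overlap between sorting rule and outcome. The wider reason to act is that the same undefined split sets the primary groups. The item should be fixed; it does not invalidate the study.

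**What to change.** In the synopsis, section 3 and section 9.4.3, or in the SAP:

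- Remove the responder versus non-responder significance test for migraine days.
- Report change in migraine days per 28 days, from run-in to each four-week period, in all treated participants, with mean and 95% CI. Under the assumptions above, the half-width for a single month is about 1.2–2.0 days at N = 36.
- Report the proportion with at least a 50% reduction, with an exact CI (33–67% for 18/36; about 34–66% for 20/40).
- Show migraine days by responder group descriptively, without a p-value or efficacy wording.
- Before outcomes are reviewed, fix one responder definition for the primary, secondary and exploratory comparisons. It should name diary migraine days as the measure, one window of the sponsor's choosing (the documents favour none), prorating for days entered, a rule for early leavers, and whether LOCF applies to a period with too few diary days.

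The cost is one between-group p-value. No new data, visits or participants are needed. IRB/IEC approval (section 10.1.1) is needed only if the protocol itself is amended rather than the SAP.

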## 4. Study Design

### 4.1. Overall Design

This is a multicenter, open label study assessing the interictal impact of fremanezumab-vfrm in participants with migraine. The study population will consist of 40 participants 18 to 65 years old, with at least 4 and up to 22 migraine days per month (inclusive) following ICHD-III criteria for migraine with or without aura.

At Visit 1, the participant will sign the informed consent indicating they are willing to participate in the study and will provide basic demographic information, have a comprehensive review of their medical history and prior and concomitant medications. The subject's migraine history will be reviewed and confirmed in accordance with the ICHD-III, by the PI or an appropriately delegated and qualified sub-Investigator. A physical and neurological examination (including vital signs) will be performed as well as a 12-lead Electrocardiography (ECG), screening comprehensive metabolic panel (CMP) labs, and the PHQ-9 will be completed. Women of childbearing potential (WOCBP) will complete a urine pregnancy test. All participants will complete the MIBS-4 questionnaire. Inclusion and Exclusion criteria will also be reviewed. Participants who meet the study criteria will be dispensed the activity tracker and its associated phone application instructions, as well as their unique Daily Headache Diary (DHD) URL and its instructions. Participants will then enter into a 28-day run-in period. During the 28-day run-in period, all participants will be monitored through the use of electronic Daily Headache Diary (DHD) to ensure they continue to meet all inclusion criteria, and none of the exclusion criteria. During this run-in period, participants will continue treating their migraines and other defined conditions with their usual treatment providing it has been stable for a minimum of 3 months. Daily electronic diaries will be used to assess symptoms and treatment response throughout the run-in period.

Visit 2 will take place 28 to 33 days following Visit 1. Those participants who (1) continue to meet eligibility criteria (2) experienced 4-22 migraine days that meet ICHD-III criteria for migraine and (3) have completed at least 23/28 diary days will be eligible to be enrolled into the study. At this visit a physical examination (including vital signs) will be performed, WOCBP will complete a urine pregnancy test, and all participants will complete the PHQ-9. Medical history and/or adverse events and concomitant medications will be reviewed and updated as needed. Participant's DHD will be reviewed for compliance, and participants will complete the following questionnaires:

- MIBS-4

This document, including any source code, is the property of [Clinvest Research LLC](#), and may contain proprietary, confidential, or legally privileged information. No part of this report, or any information contained therein, may be disseminated without the written consent of [Clinvest Research LLC](#).

- SDSF
- PROMIS-29
- MPAI-M
- BMWS
- GSE-SF

Finally, all eligible participants will receive an injection of 225 mg fremanezumab-vfrm. Participants will continue completing diary headache diaries for the remainder of the trial.

Visits 3-5 will take place on days 29 (+/-3d), 57 (+/-3d), and 85 (+/-3d), following Visit 2. At each visit: a physical examination (including vital signs) will be performed, WOCBP will complete a urine pregnancy test, and all participants will complete the PHQ-9. Medical history and/or adverse events and concomitant medications will be reviewed and updated as needed. Participant's DHD will be reviewed for compliance, and participants will complete the following questionnaires:

- MIBS-4
- SDSF
- PROMIS-29
- MPAI-M
- BMWS
- GSE-SF

Finally, all eligible participants will receive an injection of 225 mg fremanezumab-vfrm at visits 3 and 4. Visit 5 (End of Study) will not include injections but will include comprehensive metabolic panel (CMP) laboratory.

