## 9. Statistical Considerations

### 9.1. Statistical Hypotheses

The null hypothesis of this study is that participants' global Migraine Interictal Burden Scale (MIBS-4) scores will not be statistically different between 50% responders and non-responders from baseline (Visit 2) to any 4-week treatment period during the 12-week treatment period after 3 months dose of 225 mg fremanezumab-vfrm.

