#### **9.4.2. Primary endpoint**

Data for the primary endpoint will be statistically analyzed via a repeated measures ANOVA, within-between interaction comparing baseline MIBS-4 scores to treatment month(s) MIBS-4 scores between 50% responders and non-responders.

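### MIBS-4 is measured twice before the first injection, but the Visit 1 score has no stated use; both scores should enter the model, and the run-in change should be reported

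*Combined protocol and SAP*

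**What the plan says.** - **Visit 1.** Section 4.1 states "All participants will complete the MIBS-4 questionnaire". The Schedule of Activities (1.2) marks MIBS-4 at Visits 1 to 5 and at early discontinuation. The other five questionnaires start at Visit 2.
- **Visit 2.** MIBS-4 is repeated and the first injection is given at the end of the visit. On timing: "Visit 2 will take place 28 to 33 days following Visit 1".
- **Baseline.** Section 9.1 words the null hypothesis as change "from baseline (Visit 2) to any 4-week treatment period during the 12-week treatment period".
- **Primary analysis.** Section 9.4.2 specifies a repeated measures ANOVA, "within-between interaction comparing baseline MIBS-4 scores to treatment month(s) MIBS-4 scores between 50% responders and non-responders". The Visit 1 score is not part of it.
- **Design.** "This is a single-group supportive care study with one arm and no masking". No visit follows Visit 5.
- **Run-in.** Background therapy goes on: "participants will continue treating their migraines and other defined conditions with their usual treatment providing it has been stable" for at least three months.

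The eligibility criteria (5.1, 5.2) do not use MIBS-4. Section 9.4 promises a fuller SAP before database lock, but no separate SAP text is in the documents.

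**The concern.** The primary outcome is collected at a visit where no other outcome questionnaire is given, and the plan never says what that score is for. Two things may be lost.

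1. **Reference interval.** There is no control arm, and the primary comparison is between responders and non-responders. Regression to the mean, expectation or a time trend could all move MIBS-4 after Visit 2. Visit 1 to Visit 2 is the only stretch in which its movement without study drug can be seen.
2. **Precision.** A single pre-treatment score carries measurement error and short-term fluctuation. A second score can reduce that noise at no cost in participants, if it holds information that the first does not.

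The first loss is the more important. The second depends on an unknown correlation structure.

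**Working it through.** **1. The plan's own figure.** Section 9.2 gives 36 evaluable and 40 enrolled, with f = 0.25, alpha 0.05, power 0.95 and 10% withdrawal. It states neither the number of measurements m nor the correlation ρ. For a within-between interaction with two groups, the noncentrality is λ = f²·N·m/(1−ρ), with df (m−1) and (N−2)(m−1). Assuming m = 4 (Visits 2 to 5) and ρ = 0.5:

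- N = 36: λ = 0.0625 × 36 × 4 / 0.5 = 18, df 3 and 102, power 0.952.
- N = 34: λ = 17, power 0.939.
- 36/0.9 = 40.

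The stated numbers reproduce. With m = 5 (adding Visit 1) N would be 32 at the same ρ, so the calculation fits the use of Visits 2 to 5 only.

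**2. Residual variance for Visits 3 to 5, equal correlation.** Each score has variance 1 and every pair of visits has correlation ρ (assumed 0.3 to 0.7).

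- Three-visit mean, Visit 2 as covariate: (1+2ρ)/3 − ρ².
- Three-visit mean, Visits 1 and 2 as separate covariates: (1+2ρ)/3 − 2ρ²/(1+ρ).
- Visit 3 alone: 1 − ρ² against 1 − 2ρ²/(1+ρ).

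| ρ | Three-visit mean: one → two covariates | Reduction | Visit 3: one → two covariates | Reduction |
|---|---|---|---|---|
| 0.3 | 0.443 → 0.395 | 11% | 0.910 → 0.862 | 5% |
| 0.5 | 0.417 → 0.333 | 20% | 0.750 → 0.667 | 11% |
| 0.7 | 0.310 → 0.224 | 28% | 0.510 → 0.424 | 17% |

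**3. The same under AR(1).** Correlation is ρ to the power of the number of visits apart. Given Visit 2, Visit 1 then holds no further information about later visits, so two separate covariates give a ratio of 1.00 at every ρ. Averaging the two scores into one covariate does harm. For Visit 3 its residual variance is 1 − ρ²(1+ρ)/2, which at ρ = 0.5 is 0.8125 against 0.75, a ratio of 1.08. The ratios at ρ = 0.3, 0.5 and 0.7 are:

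- Visit 3: 1.04, 1.08, 1.14.
- Three-visit mean: 1.01, 1.04, 1.08.

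**4. Power.** Take 18 per group, ρ = 0.5, equal correlation and a true difference of 0.5 SD in the three-visit mean, tested two-sided at 0.05.

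- One covariate: noncentrality 0.5/√(2 × 0.417/18) = 2.32, power about 62%.
- Two covariates: 0.5/√(2 × 0.333/18) = 2.60, power about 71%.

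This is a one-degree-of-freedom contrast, not the planned interaction test. It makes no allowance for the responder groups differing in baseline score.

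**5. Precision of the run-in change.** At ρ = 0.5 with 40 participants, 20 per group:

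- Visit 2 minus Visit 1 has variance 2(1−ρ) = 1. The 95% half-width is 2.02 × √(1/40) = 0.32 SD overall, and 2.02 × √(4/40) = 0.64 SD for the difference between responder groups.
- The difference of changes, (Visit 3 − Visit 2) − (Visit 2 − Visit 1), has variance 6(1−ρ) = 3. The half-widths are 2.02 × √(3/40) = 0.55 SD and 2.02 × √(12/40) = 1.11 SD. It counts the Visit 2 score twice, which is why it is weaker.

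**The case against.** The strongest reply is that Visit 2 is a sound baseline. It is the last score before treatment and closes the 28-day diary run-in, whereas Visit 1 precedes the diary and the check on run-in migraine days. This stands, and is a reason to keep Visit 2 as the baseline for change.

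A second reply is that the gain depends on an assumption. This also stands. If correlation decays as in AR(1), Visit 1 adds nothing as a covariate and averaging costs precision.

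A third is that the promised SAP may yet use Visit 1. It may. The finding is that the documents specify no use, and that the SAP is the natural place to add one.

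A reader might infer more than the documents support:

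- **That averaging the two scores gives a 37.5% variance reduction.** That figure compares 1.333(1−ρ) with 0.833(1−ρ). It holds only for a change score on the three-visit mean under equal correlation. Under AR(1) the change-score ratios are 0.79, 0.90 and 1.005 at ρ = 0.3, 0.5 and 0.7. The endpoint is also change to each 4-week period, not to a three-visit mean.
- **That the run-in is an untreated control.** Usual acute treatment and stable preventives continue, and the interval comes before treatment in the same people. It is a reference period without study drug.

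**Conclusion.** The point holds as a cheap improvement. MIBS-4 is collected twice before the first injection, only Visit 2 has a role, and the single interval without study drug is left unused. The stated sample size reproduces under the assumed m and ρ, and choosing Visit 2 as baseline is not an error.

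The likely precision gain from a second, separate covariate runs from 0% under AR(1) to 11–28% of residual variance for the three-visit mean (5–17% for Visit 3) under equal correlation. Equal correlation with ρ = 0.5 is one setting that reproduces the plan's sample size, but the documents do not state it. The comparison is with Visit 2 alone as covariate, so any effect of moving from the planned ANOVA to a covariate model is not part of it.

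The overall run-in change would be usefully described, at about ±0.32 SD. The by-group figure, about ±0.64 SD, can be shown but will settle little.

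**What to change.** In section 9.4.2 and the SAP:

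1. Keep Visit 2 as the baseline for change, as section 9.1 has it.
2. Model MIBS-4 at Visits 3 to 5 with the Visit 1 and Visit 2 scores as two separate covariates. Do not replace the baseline by their average.
3. Pre-specify a descriptive estimate, with 95% confidence interval, of the Visit 1 to Visit 2 change, overall and by responder group, shown beside the treatment-period changes. State that it is a within-person reference without study drug, with usual treatment continuing, and not a concurrent control.
4. Do not make the difference of changes a formal test, given its width.

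The cost is one degree of freedom, some additional analysis and an imprecise by-group run-in estimate. No participant, visit or data item is added.
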